##### 10.2.2 Primary Safety Endpoint

The primary safety endpoint is the adverse event (AE) rate: the number of AEs per 100 treatments occurring in the home phase of the study, compared with those occurring in the in-clinic phase. All AEs will be collected, summarized by phase of the study, and compared between the in-clinic and in-home phase of the study. Additionally, in accordance with NCT02460263 (Plumb 2020), the rate of pre-specified AEs will be compared between treatment groups, with the pre-specified AEs comprising the following components:

- Serious adverse event: any adverse event that resulted in death, was life-threatening, required hospitalization or prolonged existing hospitalization, required intervention to

prevent permanent impairment or damage, or resulted in persistent or significant disability/incapacity.

- Allergic reaction: type A anaphylactoid or type B dialyzer reactions to dialyzer, blood tubing, or chemical disinfectant.
- Blood loss: blood loss resulting in hemodynamic compromise that led to death, transfusion, or fluid resuscitation with greater than 1 liter of crystalloid IV fluids.
- Hemolytic Reaction: hemolytic reactions due to disinfectant exposure, dialysate temperature, mechanical failure, or other device related causes.
- Infection: any infection related to hemodialysis catheter, its tunnel or exit site, arteriovenous fistula (AVF), or arteriovenous graft (AVG).
- Intradialytic event: a significant clinical event such as loss of consciousness, cardiac arrest, or seizure caused by device failure.
- Vascular access complication: defined as AVF or AVG clotting during the dialysis procedure, bleeding for more than 30 minutes post-dialysis for 3 consecutive sessions, difficulty with vascular access resulting in inability to initiate or complete dialysis treatments or complications related to hemodialysis catheters (not including reduced blood flow in catheter or tissue plasminogen activator (TPA) or catheter exchange).
- Pyrogenic reaction: onset of objective chills (visible rigors) and fever (oral temperature greater than or equal to 37.5 degrees Celsius) in a participant who was afebrile and who had no recorded signs or symptoms of infection before treatment.

Due to a lack of published data on the overall AE rate, power calculations were performed using assumptions for the pre-specified AE rate per 100 treatments. A 95% confidence interval for the number of AEs per 100 dialysis treatments in each treatment period (In-Center and In-Home use) will be constructed as outlined in Section 10.4.2 below. Similarly, the 95% CI for the difference in number of AEs per 100 treatments in each treatment period will be calculated. The power calculations were done based on the following assumptions:

- $\mu_{IH} = 0.03$ , the rate of AEs per dialysis treatment in-Home is 0.03
- $\mu_{IC} = 0.03$ , the rate of AEs per dialysis treatment in-Center is 0.03
- $\mu_{IH} - \mu_{IC} = 0$ , the difference in rate of AEs per dialysis treatment is 0
- $\sigma_{IH-IC} \leq 0.17$ , the standard deviation of the difference is less than 0.17 AEs per dialysis interval
- Non-inferiority margin of 0.1 AEs per dialysis interval
- One-sided  $\alpha=0.025$

Using a two-sample t-test, a sample size of n=33 patients with 4 dialysis intervals per week for 8 weeks, (i.e., 33 patients with 32 treatments, for a total of 1056 treatments) would have >90% power to demonstrate the rate of AEs per 100 treatments is no more than 10% higher in the In-Home period versus the In-Center period. While the primary safety endpoint will be tested using the methods outlined in Section 10.4.2, we are confident that we are adequately powered to detect the difference once taking into account the repeated measures within participant.

To account for an expected 15% lost to follow-up rate, and an additional 2 expected death or transplant events during the 8 week In-Home phase (based on a combined rate of death and transplant of approximately 15 per 100 patient-years in a usual HHD population), a total of 50 patients will be enrolled to yield the 33 evaluable patients needed to be sufficiently powered for both the primary efficacy and primary safety endpoints.

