4 SAMPLE SIZE

Sample size for analysis of primary effectiveness endpoint was calculated using a one-sample test. It was determined that a sample of n=11 patients, each measures weekly for 8 weeks of treatment, will have >90% power to detect that the mean weekly standard Kt/V is greater than 2.1. Sample size was calculated under the following assumptions:

- True treatment period mean weekly standard Kt/V is 2.5
- Standard deviation is 0.7
- One-sided $\alpha=0.025$
- Within patient correlation of $\rho=0.50$
- AR(1) covariance structure

Sample size for primary safety endpoint was calculated using a two-sample t-test. It was determined that a sample size of n=33 patients, with 4 dialysis intervals per week for 8 weeks, would have >90% power to demonstrate the rate of AEs per 100 treatments is no more than 10% higher in the in-home period compared to the in-center period. Sample size was calculated under the following assumptions:

- $\mu_{IH} = 0.03$, the rate of AEs per dialysis treatment in-Home is 0.03
- $\mu_{IC} = 0.03$, the rate of AEs per dialysis treatment in-Center is 0.03
- $\mu_{IH} - \mu_{IC} = 0$, the difference in rate of AEs per dialysis treatment is 0
- $\sigma_{IH-IC} \leq 0.17$, the standard deviation of the difference is less than 0.17 AEs per dialysis interval
- Non-inferiority margin of 0.1 AEs per dialysis interval
- One-sided $\alpha=0.025$

To account for an expected 15% lost to follow-up rate, and an additional 2 expected death or transplant events during the 8 week in-home phase, based on a combined rate of death and transplant of approximately 15 per 100 patient-years in a usual home hemodialysis (HHD) population, up to 50 patients will be enrolled to yield the 33 evaluable patients needed to be sufficiently powered for both the primary efficacy and primary safety endpoints.

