7.5 MULTIPLE COMPARISONS AND MULTIPLICITY

For the trial to be considered a success, the null hypothesis must be rejected for both co-primary effectiveness endpoints, as well as for the primary safety endpoint. The co-primary effectiveness endpoints will each be tested at the one-sided $\alpha=0.025$ level of significance, where the one-sided alternative hypothesis represents a mean standardized weekly Kt/V of greater than or equal to 2.1, for both the in-clinic and in-home phases of the study, respectively. The primary safety endpoint will also be tested at the one-sided $\alpha=0.025$ level of significance, where the one-sided alternative hypothesis represents non-inferiority of the in-home adverse event rate to the in-clinic adverse event rate, under a non-inferiority margin of 10%. No adjustments for multiple comparisons will be made for the primary endpoints.

All secondary effectiveness and safety endpoints will be descriptive in nature and 95% confidence intervals will be presented. No adjustments for multiplicity will be made.

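### The >90% safety power in SAP 4 rests on pre-specified AEs, not on the all-AE comparison that decides success, and the stated losses do not lead to 50 enrolled

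*Protocol*

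**What the plan says.** **Power inputs.** Protocol 10.2.2 says that "power calculations were performed using assumptions for the pre-specified AE rate per 100 treatments", and gives the lack of published overall AE data as the reason. The inputs are a rate of 0.03 per treatment in each period, a true difference of 0, a margin of 0.1, one-sided alpha 0.025, and 0.17 described as "the standard deviation of the difference is less than 0.17 AEs per dialysis interval". The calculation reads "Using a two-sample t-test, a sample size of n=33 patients with 4 dialysis intervals per week for 8 weeks", counted as "33 patients with 32 treatments, for a total of 1056 treatments", with >90% power. For the analysis that will actually be run, the protocol gives no figure: "While the primary safety endpoint will be tested using the methods outlined in Section 10.4.2, we are confident that we are adequately powered".

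**SAP 4.** It says "Sample size for primary safety endpoint was calculated using a two-sample t-test" and lists the same inputs, for example "the rate of AEs per dialysis treatment in-Home is 0.03". It does not say that they refer to pre-specified AEs.

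**What is tested.** SAP 7.5 requires for success that "the null hypothesis must be rejected for both co-primary effectiveness endpoints, as well as for the primary safety endpoint". Under Protocol 10.4.2 and SAP 10.1 the safety test compares all AEs per 100 treatments in a Poisson GEE model. SAP 10.1 keeps the pre-specified AEs descriptive, without a formal test.

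**Enrolment.** Both documents go from 33 evaluable to 50 by allowing for 15% loss to follow-up and 2 deaths or transplants in the 8-week home phase, at about 15 per 100 patient-years. The protocol enrols 50; SAP 4 and SAP 13 say up to 50.

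**The concern.** The safety comparison is one of the conditions for success, so its power statement should refer to the endpoint tested and follow from its inputs. All AEs include the pre-specified ones, so their rate can only be equal or higher, and variance normally rises with the rate. Power computed at 3 events per 100 treatments therefore does not carry over to all AEs. Someone who reads SAP 4 alone would take >90% as the power of the deciding test. Separately, the enrolment figure does not follow from the losses said to justify it, and the named test does not plainly match the kind of SD given.

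**Working it through.** **Inputs.** From Protocol 10.2.2 and SAP 4: n=33, margin 0.1, true difference 0, SD 0.17, one-sided alpha 0.025, rate 0.03, 15% loss, 2 events, 15 per 100 patient-years, 8 weeks. From Protocol 6.5: the in-clinic phase lasts 4 to 8 weeks, which at 3 sessions per week is 12 to 24 treatments (or facility standard); the home phase has 4 × 8 = 32. The count of 33 × 32 = 1056 therefore covers the home phase only.

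**Step 1. Reproduce >90%** (noncentral t).
- Paired t, SD of the difference 0.17: noncentrality 0.1/(0.17/√33), power 90.6%. At n=32 it is 89.7%, so 33 is the smallest n that reaches 90%.
- Two-sample t, 33 values per period, per-period SD 0.17/√2 = 0.120 (periods assumed independent): 91.4%.

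At the label the documents use, the figure is reproduced by either route. The exact match at 33 suggests a paired calculation, but the documents do not say so. The unit is also open. A single-treatment SD at this rate would be √(0.03 × 0.97) = 0.171, which would fit the phrase about dialysis intervals. No source for 0.17 is given.

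**Step 2. Power for all AEs.** The documents give no all-AE rate, SD or overdispersion, so only an assumed range can be shown. As an approximation to the GEE test, I used a paired t-test on participant-level rates with n=33 and margin 0.1. The SD of the difference is √(φ × rate × (1/32 + 1/m)), where m is the number of clinic treatments and φ the overdispersion. The same rate is assumed in both periods.

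| Rate per treatment | φ | SD, m=12 | Power, m=12 | SD, m=24 | Power, m=24 |
|---|---|---|---|---|---|
| 0.03 (documents) | 1 | 0.059 | >99.9% | 0.047 | >99.9% |
| 0.1 (assumed) | 1 | 0.107 | 99.9% | 0.085 | >99.9% |
| 0.2 (assumed) | 1 | 0.151 | 96% | 0.121 | 99.6% |
| 0.2 (assumed) | 2 | 0.214 | 74% | 0.171 | 90% |
| 0.3 (assumed) | 1 | 0.185 | 85% | 0.148 | 96% |
| 0.5 (assumed) | 1 | 0.239 | 64% | 0.191 | 83% |

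By SD alone, power is 80% at 0.20, 61% at 0.25 and 46% at 0.30. With m=12 those SDs need about 35, 55 and 79 AEs per 100 treatments under plain Poisson variation, or 17, 27 and 39 with twofold overdispersion.

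**Step 3. Enrolment.**
- 33/0.85 + 2 = 40.8, so 41; or (33 + 2)/0.85 = 41.2, so 42.
- In the other direction, 50 × 0.85 − 2 = 40.5 and (50 − 2) × 0.85 = 40.8 evaluable, not 33. Going from 50 to 33 implies 34% total loss.
- Events over 8 weeks: 0.15 × 33 × 8/52 = 0.76; 0.15 × 50 × 8/52 = 1.15.
- With 1 event: 33/0.85 + 1 = 39.8 or 34/0.85 = 40.0, so 40.
- Over the minimum 13 weeks of treatment (4 clinic, 1 transition, 8 home): 0.15 × 50 × 13/52 = 1.9 events, close to 2.

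**The case against.** The protocol is open about the substitution and its reason. The SAP was prepared from the protocol, and its list of departures in SAP 13 names no change to the power assumptions. A missing all-AE estimate is an acknowledged gap. That stands as regards the protocol. It does not help SAP 4, which labels the inputs simply as AE rates, and a lack of published data does not prevent a sensitivity range.

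The SDs of 0.20 to 0.30 have no source in the documents, and under plain Poisson variation they need 12 to 26 times the documented rate of 3 per 100. That also stands: those power figures are illustrations from a paired t-test, not the power of the GEE test.

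The figure of 2 events may be sound and the 8-week period the slip, because about 13 weeks in 50 patients gives 1.9. The text as written still ties 2 events to the 8-week home phase. The plan also has routes out of the evaluable set that the derivation omits: failed training competency, missed treatments, and the 75% rule in SAP 6.2. These may justify 50, but no figure is given for them.

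Two stronger readings are tempting. One is that the true power is only 65.3%. That is what a two-sample t-test gives with 0.17 as the SD in each period, but neither document describes 0.17 that way; both call it the SD of the difference. The other is that the safety test is underpowered. Step 2 shows that adequate and inadequate power are both possible, and the documents give nothing to choose between them.

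**Conclusion.** The point holds in three parts of unequal weight.

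1. **Endpoint (main part).** The >90% applies to assumptions for pre-specified AEs, which are not formally tested. The all-AE comparison that decides success has no stated power, and SAP 4 does not say so. Whether that comparison is underpowered cannot be determined from the documents.
2. **Enrolment.** The stated losses give 41 to 42, not 50, and the stated event rate over the stated 8 weeks gives about 1 event (0.8 to 1.2), not 2. There is no shortfall: 50 exceeds the need and is a ceiling in the SAP. Only the derivation is wrong.
3. **Test and SD (minor).** The >90% is not shown to be wrong, since it is reproduced at the label given. The name of the test and the unit of the SD need to be made consistent.

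The power figures assume normal-theory tests on participant-level rates. Those for all AEs also assume a constant common rate and the overdispersion shown.

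**What to change.** In Protocol 10.2.2 and SAP 4:

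- **(a) Endpoint.** State that >90% applies only to the pre-specified AE assumptions, and repeat the protocol's disclosure in SAP 4. Add a range of power for the all-AE comparison over the sponsor's own assumed rates and overdispersion, with 32 home and about 12 to 24 clinic treatments, labelled as an approximation to the GEE test. The 80%, 61% and 46% at SDs of 0.20, 0.25 and 0.30 show the form; they are not values to prescribe.
- **(b) Enrolment.** Make the derivation consistent in one of two ways. Either keep 2 events, state 41 to 42, and change the exposure period to one that yields 2 (about 13 weeks in 50 patients); or keep the 8-week phase with about 1 event and state 40. Mixing the two would create a new error. Then name the further losses (failed training competency, missed treatments, the 75% rule) that justify a ceiling of 50.
- **(c) Test and SD.** Name the test that matches 0.17 (a paired t-test if it is the participant-level SD of the difference), and state its unit and source.

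The cost is text in two sections plus a short sensitivity calculation. No patients, visits or trial analyses are added. The safety power claim becomes conditional on the variability assumed for all AEs.

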Statistical overview	
The study will be considered a success from a statistical standpoint if:
 
 
1. Both primary effectiveness variables pass their respective hypotheses, i.e., <math>Ha_0</math> and <math>Hb_0</math> below are rejected in favor of <math>Ha_1</math> and <math>Hb_1</math>, respectively, and
 
2. The rate of adverse events per 100 treatments is not worse during the In-Home period as compared to the In-Center period.
 
 
Summary statistics will be provided for all baseline characteristics and endpoints. The primary effectiveness endpoint will be tested using the Least Squares Mean from a repeated measures analysis of variance (ANOVA) model. A 95% confidence interval will be computed for the primary safety endpoint for each treatment period using the Least Squares Mean from a repeated measures GEE model. All hypothesis testing will be performed at a two-sided <math>\alpha=0.05</math> level unless otherwise specified.
 
The primary analysis of the primary effectiveness and primary safety endpoints will be performed on all enrolled patients with available data. A sensitivity analysis will be performed for the primary

	effectiveness endpoint using multiple imputation. No imputation will be performed for the primary safety endpoint or any secondary endpoints.
US Agent (Sponsor)	QDT Inc. [name]

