#### 10.4.2 Primary Safety Endpoint

The primary safety endpoint is the adverse event rate: the number of adverse events per 100 treatments occurring in the in-clinic portion of the study compared with those occurring in the home portion.

For each treatment period, a 95% confidence interval will be computed on the AE rate per 100 treatments. This confidence interval will be computed using the least squares mean for the respective treatment period from a repeated measures GEE model containing terms for participant, treatment arm and time points using a Poisson link function and AR(1) covariance structure.

Additionally, to compare the AE rate between treatment periods, the difference in number of AEs between treatment periods and the associated 95% CI of the difference will be computed using the least squares means from the above GEE model. The difference in LS means will be used to test the following hypothesis at a one-sided  $\alpha=0.025$  level of significance:

$$H_{c0}: \mu_{IH} - \mu_{IC} \geq 0.1 \text{ vs. } H_{c1}: \mu_{IH} - \mu_{IC} < 0.1$$

If the upper bound of the 95% CI for the difference between number of AEs between treatment periods is below 10%, the AE rate for the In-Home treatment period will be considered not worse than the AE rate for the In-Center treatment period.

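### The power sentence for the primary safety endpoint words an absolute margin of 0.1 AEs per treatment as 10% higher; the claimed >90% power holds only for the absolute margin

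*Protocol*

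**What the plan says.** The assumptions in Protocol 10.2.2 include a "Non-inferiority margin of 0.1 AEs per dialysis interval", a rate of 0.03 AEs per treatment in each period, a true difference of zero, one-sided alpha of 0.025, and a limit on variability described as "the standard deviation of the difference is less than 0.17 AEs per dialysis interval". The result is introduced with "Using a two-sample t-test, a sample size of n=33 patients" and is said to give more than 90% power to "demonstrate the rate of AEs per 100 treatments is no more than 10% higher in the In-Home period versus the In-Center period". SAP 4 repeats the assumptions and the power sentence.

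Protocol 10.4.2 and SAP 10.1 set up the test as a home-minus-clinic difference against 0.1, with no unit attached to the 0.1. The decision rule that follows begins "If the upper bound of the 95% CI for the difference between number of AEs between treatment periods is below 10", and a percent sign comes next. SAP 7.5 also gives the margin as 10%. The success criterion in the Protocol synopsis, repeated in Protocol 10.4 and SAP 9.1, is: "The rate of adverse events per 100 treatments is not worse during the In-Home period as compared to the In-Center period".

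Protocol 10.2.2 explains that the 0.03 is a rate for pre-specified AEs, used "Due to a lack of published data on the overall AE rate". SAP 10.1 says that pre-specified AEs will not be formally tested; the formal test is on all AEs.

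**The concern.** An AE rate per treatment is a count rate, so a percentage attached to it has no natural absolute meaning. To most readers, 10% higher means a home rate of at most 1.1 times the clinic rate. An absolute margin of 0.1 per treatment is a different rule. The two coincide only where 10% of the clinic rate equals 0.1, that is at 1.0 AE per treatment, about 33 times the assumed 0.03.

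Two things are at stake. First, the stated power belongs to one margin and the sentence describes another. Second, this margin decides the safety half of trial success, so a reader of the result could take a pass to mean much closer agreement between home and clinic than the test requires.

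**Working it through.** **Inputs (Protocol 10.2.2, repeated in SAP 4).** n = 33; SD of the difference 0.17; one-sided alpha 0.025; true difference 0; clinic and home rates 0.03 per treatment; margin 0.1 per treatment.

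**1. Reproduce the plan's power.** Treat 0.17 as the SD of within-patient differences (paired t, 32 degrees of freedom).

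- Standard error = 0.17/√33 = 0.0296
- Noncentrality = 0.1/0.0296 = 3.38
- Critical value t(0.975, 32) = 2.037
- Power from the noncentral t = 90.6%

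Thirty-three is the smallest n that reaches 90% on this calculation. The plan's figure is therefore right for the absolute margin.

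**2. Power for the sentence as worded.** Ten percent of 0.03 is 0.003 per treatment.

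- Noncentrality = 0.003/0.0296 = 0.10
- Power = 3.1%

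Other set-ups for a 10% relative margin do not rescue the sentence:

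| Set-up | Power |
|---|---|
| Two-sample t, 33 per period, SD 0.17 | 2.9% |
| Treatments as units, 1056 home vs 396 clinic (33 × 3 × 4 weeks, assumed) | 4.8% |
| Treatments as units, 1056 vs 1056 | 6.0% |
| One-sample t, 1056 treatments | 8.3% |
| Poisson log rate ratio, margin 1.10, 1056 vs 396 treatments | 4.6% |
| Poisson log rate ratio, margin 1.10, 1056 vs 1056 treatments | 5.7% |

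**3. What the absolute margin allows.** Boundary ratio = (clinic rate + 0.1)/clinic rate.

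| Clinic rate per 100 | Basis | Home rate at null boundary, per 100 | Ratio |
|---|---|---|---|
| 3 | Plan's pre-specified AE rate | 13 | 0.13/0.03 = 4.3 |
| 10 | Assumed all-AE rate | 20 | 0.20/0.10 = 2.0 |
| 20 | Assumed all-AE rate | 30 | 0.30/0.20 = 1.5 |

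At 3 per 100, a 10% relative limit would instead be 3 × 1.1 = 3.3 per 100.

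**4. Scale of the comparison.** Protocol 10.4.2 and SAP 10.1 take least squares means from a GEE with what they call a Poisson link and compare their difference with 0.1. If that means a log link and the means are left on the log scale, 0.1 corresponds to a rate ratio of exp(0.1) = 1.105, which is close to the 10% wording. Protocol 10.2.2 points to the rate scale ("the 95% CI for the difference in number of AEs per 100 treatments in each treatment period will be calculated"), and SAP 10.1 refers to a difference in rates for the pre-specified AEs. No section says that the means are back-transformed first.

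**The case against.** The strongest reply is that the plan contains no calculation error. The absolute margin stands in the list just above the power sentence, the hypotheses are written as a difference against 0.1, and the claimed power reproduces. The 3% is the power of a test that no section plans. All of this stands: the error lies in the wording of the claim, and the correction leaves the intended test as it is.

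A reader might go further in several ways that the documents do not support:

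- **That all the percent wordings are equally wrong.** Only Protocol 10.2.2 and SAP 4 read naturally as relative. In Protocol 10.4.2 and SAP 10.1 the 10% is applied to the interval for a difference, directly after the 0.1 hypothesis, and in SAP 7.5 it is loose shorthand for the same margin. These places need a unit.
- **That *not worse* is undefined.** Protocol 10.4.2 and SAP 10.1 define it by the upper confidence limit, and SAP 9.1 points to SAP 10.1. The definition is only as clear as the margin in it.
- **That the trial is underpowered because a two-sample test is named.** A two-sample t-test with SD 0.17 in each period would give 65.3%, but 0.17 is defined as the SD of the difference. The claim reproduces as a paired test (90.6%), or as a two-sample test with a per-period SD of 0.17/√2 (91.4%). This is a matter of labelling.
- **That the test itself allows a 4.3-fold excess.** That ratio uses the pre-specified AE rate, which is not formally tested. The visible text gives no all-AE rate, and the ratio shrinks as the rate rises.
- **That the margin has no rationale.** Part of the prior-experience section was not available for review, so this cannot be concluded.

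**Conclusion.** The point holds for the power sentence in Protocol 10.2.2 and SAP 4. More than 90% power is correct for an absolute margin of 10 AEs per 100 treatments (90.6%) and false for a home rate at most 10% higher at the assumed 0.03 (3.1%; 3% to 8% across the set-ups tried). These figures rest on the plan's own n, SD, rate and alpha. The 4.3-fold boundary rests on the plan's rate for pre-specified AEs; the 2.0-fold and 1.5-fold boundaries rest on assumed all-AE rates.

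The correction is needed because a stated power claim and the description of a success threshold are wrong as written. The missing statement on scale supports the same correction, since a log-scale comparison with 0.1 would test a ratio of 1.105. Neither the sample size nor the intended absolute test is shown to be wrong.

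**What to change.** 1. In Protocol 10.2.2 and SAP 4, reword the power claim so that the home rate is shown to be *no more than 10 AEs per 100 treatments (0.1 per treatment) higher, as an absolute difference*.
2. In Protocol 10.4.2 and SAP 7.5 and 10.1, replace 10% with the same absolute margin and unit, so that *not worse* is tied to it.
3. In Protocol 10.4.2 and SAP 10.1, state that the GEE least squares means are back-transformed, and that the difference and its 95% CI are on the rate scale before comparison with 0.1.

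The cost is a wording change in five sections and one sentence on scale. The stated safety claim will read less favourably. Enrolment and the intended test are unchanged.

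Describing the power calculation as paired, adding power for assumed all-AE rates, and setting out the margin rationale beside the sample size would help a reader, but they are optional.
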